7.3. Analysis of the Key Secondary Efficacy Parameters

7.3.1. Key Secondary Efficacy Measures

7.3.1.1. Itch Numerical Rating Scale Score

The Itch NRS is a once-per-24 hours ("daily") patient-reported measure of itch intensity assessed using an 11-point scale (0 = no itch to 10 = worst imaginable itch). Participants will be asked to record their highest (worst) level of itch in the evening over the 24-hour recall period.

The Itch NRS score for baseline will be determined by averaging the 7 daily NRS scores before Day 1 (Day -7 to Day -1). The by-visit Itch NRS score for postbaseline visits will be determined by averaging the 7 daily NRS scores before the visit day. If 4 or more daily scores are missing (out of the 7), the Itch NRS score at the visit will be set to missing.

The proportion of participants with a clinically relevant change in itch – defined as a ≥ 4 -point improvement in Itch NRS score from baseline to Week 8 – will be summarized by treatment groups for participants with baseline Itch NRS ≥ 4 .

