7.4.1.6. Dermatology Life Quality Index and Children's Dermatology Life Quality Index

The DLQI ([Finlay and Khan 1994](#)) is a simple 10-question validated questionnaire for use in participants aged 16 years and over to measure how much the skin problem has affected the participant over the previous 7 days.

The scoring of each question is as follows: Very much = 3; A lot = 2; A little = 1; Not at all = 0; Not relevant = 0; Question 7, “Prevented work or studying” = 3.

The following imputation will be applied for incorrectly completed questionnaires:

- If 1 question is left unanswered, this is scored 0 and the scores are summed and expressed as usual out of a maximum of 30.
- If 2 or more questions are left unanswered, the questionnaire is not scored.
- If question 7 is answered “yes,” this is scored 3. If Question 7 is answered “no,” but then either “a lot” or “a little” is ticked, this is then scored 2 or 1. If “Not relevant” is ticked, the score for Question 7 is 0. If it is answered “no,” but the second half is left incomplete, the score will remain 0.
- If 2 or more response options are ticked, the response option with the highest score should be recorded.
- If there is a response between 2 tick boxes, the lower of the 2 score options should be recorded.
- For DLQI 6 subscales, if the answer to one question in a subscale is missing, that subscale should not be scored.

The DLQI is calculated by summing the score of each question resulting in a maximum of 30 and a minimum of 0. The higher the score, the more quality of life is impaired.

The meaning of total DLQI scores can be categorized as follows:

- 0 to 1 = No effect
- 2 to 5 = Small effect
- 6 to 10 = Moderate effect
- 11 to 20 = Very large effect
- 21 to 30 = Extremely large effect

A change from baseline in DLQI and CDLQI score of at least 4 points is considered clinically important (Basra et al 2015, Waters et al 2010).

The questionnaire is also analyzed under 6 sub-scales as follows:

- Symptoms and feelings (Questions 1 and 2)
- Daily activities (Questions 3 and 4)
- Leisure (Questions 5 and 6)
- Work and school (Question 7)
- Personal relations (Questions 8 and 9)
- Treatment (Question 10)

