CDLQI (Lewis-Jones and Finlay 1995) is the youth/children's version of the DLQI and will be completed by adolescents aged ≥ 12 years to < 16 years. The scoring of each question is Very much = 3; Quite a lot = 2; Only a little = 1; Not at all = 0; Question unanswered = 0; Question 7: "Prevented school" = 3. The CDLQI is calculated by summing the score of each question resulting in a maximum of 30 and a minimum of 0. The higher the score, the more quality of life is impaired.

The questionnaire is also analyzed under 6 subscales as follows:

- Symptoms and feelings (Questions 1 and 2)
- Leisure (Questions 4, 5, and 6)
- School or holidays (Question 7)
- Personal relationships (Questions 3 and 8)
- Sleep (Question 9)
- Treatment (Question 10)

The severity banding for CDLQI scores:

- 0 to 1 = No effect on child's life
- 2 to 6 = Small effect
- 7 to 12 = Moderate effect

- 13 to 18 = Very large effect
- 19 to 30 = Extremely large effect

The following imputation will be applied for incorrectly completed questionnaires for CDLQI:

1. If one question is left unanswered, this is scored 0, and the scores are summed and expressed as usual out of a maximum of 30.
2. If 2 or more questions are left unanswered, the questionnaire is not scored.
3. If both parts of Question 7 are completed, the higher of the 2 scores should be counted.

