7.4.2. Secondary Efficacy Analysis

All secondary efficacy analyses will be conducted based on the ITT population in the VC and LTS periods.

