7.4.2.3. Categorical Efficacy Endpoints

For the following categorical parameters, summary statistics including sample size, frequency, and percentages will be presented by visits.

- Proportion of participants achieving an IGA of 0 or 1
- Proportion of participants with a \geq 2-point improvement in Itch NRS score
- Proportion of participants with a \geq 3-point improvement in Itch NRS score
- Proportion of participants with a \geq 4-point improvement in Itch NRS score
- Proportion of participants achieving EASI50
- Proportion of participants achieving EASI75

- Proportion of participants achieving EASI90
- Proportion of participants with a \geq 6-point improvement in the PROMIS Short Form (8a) – Sleep-Related Impairment 24-hour recall score
- Proportion of participants with a \geq 6-point improvement in the PROMIS Short Form (8b) – Sleep Disturbance 24-hour recall score
- Proportion of participants with a score of either 1 or 2 of PGIC
- Proportion of participants with a clinically meaningful improvement (\geq 4-point improvement) in DLQI/CDLQI

A logistic regression model with treatment and stratification factors as covariates will be fit at Week 8. The p-values between each ruxolitinib group versus vehicle will be calculated based on Wald test. Exact logistic regression will be used for all of the comparisons if any of the dose levels have an expected cell count less than 5. The NRI will be used to impute postbaseline missing values for binary outcomes based on IGA, EASI, Itch NRS, PROMIS Short Form – Sleep-Related Impairment (8a) scores, PROMIS Short Form – Sleep Disturbance (8b) scores.

For the following categorical endpoints, the number and percentage of participants will be summarized by treatment at each postbaseline visit.

- Proportion of participants in each category of EASI score
- Proportion of participants in each category of IGA score
- Proportion of participants in each category of PGIC score
- Proportion of participants in each category of POEM score
- Proportion of participants in each category of DLQI/CDLQI score
- Proportion of participants in each category of each EQ-5D dimension

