2.5.2.1	Summary and Analysis of By-Visit PROMIS Sleep-Related Impairment Score (8a) From Baseline to Week 52	ITT

Table No.	Title	Population
2.5.2.2	Summary of By-Visit PROMIS Sleep-Related Impairment Score (8a) in LTS Period	ITT
2.5.3	Summary and Analysis of Daily PROMIS Sleep-Related Impairment Score (8a) in VC Period	ITT
SCORAD		
2.6	Summary and Analysis of SCORAD Score in VC Period	ITT
Skin Pain NRS Score		
2.7.1	Summary and Analysis of By-Visit Skin Pain NRS Score in VC Period	ITT
2.7.2	Summary and Analysis of Daily Skin Pain NRS Score in VC Period	ITT
BSA		
2.8.1.1	Summary and Analysis of Total %BSA Afflicted by AD From Baseline to Week 52	ITT
2.8.1.2	Summary of Total %BSA Afflicted by AD in LTS Period	ITT
POEM		
2.9.1.1	Summary and Analysis of Total POEM Score From Baseline to Week 52	ITT
2.9.1.2	Summary of Total POEM Score in LTS Period	ITT
2.9.2.1	Summary of Participants in Each Category of POEM Score From Baseline to Week 52	ITT
2.9.2.2	Summary of Participants in Each Category of POEM Score in LTS Period	ITT
DLQI/CDLQI		
2.10.1.1	Summary and Analysis of Total DLQI Score From Baseline to Week 52	ITT
2.10.1.2	Summary and Analysis of Total CDLQI Score From Baseline to Week 52	ITT
2.10.1.3	Summary of Total DLQI Score in LTS Period	ITT
2.10.1.4	Summary of Total CDLQI Score in LTS Period	ITT
2.10.2.1	Summary and Analysis of DLQI Subscore From Baseline to Week 52	ITT
2.10.2.2	Summary and Analysis of CDLQI Subscore From Baseline to Week 52	ITT
2.10.2.3	Summary of DLQI Subscore in LTS Period	ITT
2.10.2.4	Summary of CDLQI Subscore in LTS Period	ITT
2.10.3.1	Summary of Participants in Each Category of DLQI Score From Baseline to Week 52	ITT
2.10.3.2	Summary of Participants in Each Category of CDLQI Score From Baseline to Week 52	ITT
2.10.3.3	Summary of Participants in Each Category of DLQI Score in LTS Period	ITT
2.10.3.4	Summary of Participants in Each Category of CDLQI Score in LTS Period	ITT
2.10.4.1	Summary and Analysis of Participants Achieving ≥ 4 Improvement in DLQI Score From Baseline to Week 52	ITT
2.10.4.2	Summary and Analysis of Participants Achieving ≥ 4 Improvement in CDLQI Score From Baseline to Week 52	ITT
2.10.4.3	Summary of Participants Achieving ≥ 4 Improvement in DLQI Score in LTS Period	ITT
2.10.4.4	Summary of Participants Achieving ≥ 4 Improvement in CDLQI Score in LTS Period	ITT
PGIC		
2.11.1	Summary and Analysis of Participants Achieving a PGIC Score of 1 or 2 in VC Period	ITT

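### The Week 8 ≥ 4-point DLQI and CDLQI responder analyses set no minimum baseline, so participants who start at 0 to 3 cannot respond and dilute the comparison equally in every arm

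*SAP*

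**What the plan says.** SAP 7.4.1.6 gives the threshold: "A change from baseline in DLQI and CDLQI score of at least 4 points is considered clinically important". It also gives the range of each scale: "The DLQI is calculated by summing the score of each question resulting in a maximum of 30 and a minimum of 0", and "The CDLQI is calculated by summing the score of each question resulting in a maximum of 30 and a minimum of 0". A higher score means a worse quality of life, so improvement is a fall.

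SAP 7.4.2.3 lists, among the categorical endpoints, "Proportion of participants with a clinically meaningful improvement" in DLQI/CDLQI, defined as at least 4 points. It attaches no baseline condition. The same section plans a logistic regression at Week 8 with treatment and stratification factors, and Wald p-values for each dose against vehicle. On the analysis set, SAP 7.4.2 states: "All secondary efficacy analyses will be conducted based on the ITT population in the VC and LTS periods". SAP 5.3.1 defines ITT as all randomized participants. Protocol 5.1 sets no minimum DLQI or CDLQI for entry.

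For the ≥ 4-point itch response, SAP 7.3.1.1 does set a condition: the proportion "will be summarized by treatment groups for participants with baseline Itch NRS ≥ 4".

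Appendix A lists four tables for the DLQI/CDLQI response. Table 2.10.4.1 is titled "Summary and Analysis of Participants Achieving ≥ 4 Improvement in DLQI Score From Baseline to Week 52", and Table 2.10.4.2 is its CDLQI counterpart; both are titled as summary and analysis. Tables 2.10.4.3 and 2.10.4.4, for the LTS period, are titled as summary only.

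**The concern.** A participant whose baseline is 0, 1, 2 or 3 can fall by at most 3 points. That person cannot be a responder, whatever the cream does, and still counts in the denominator of a proportion described as clinically meaningful improvement.

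Low baselines are plausible here. Entry allows mild disease (IGA 2, up to about 25% of participants) and affected BSA from 3%. The SAP's own DLQI bands call 0 to 1 no effect and 2 to 5 a small effect.

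Three things are at stake, all within this one analysis. The reported response rates and their difference are smaller than among participants able to respond. The odds ratio sits closer to 1. The planned Wald test has less power than the same data could give. The result would also be read beside an itch response built on a different kind of denominator.

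**Working it through.** **Plan's own figure.** The documents state no rate, sample size or power for DLQI or CDLQI response. The only stated power is for IGA-TS: above 95% with 45% and 30% against 10%, Fisher exact test, two-sided 0.025. With 600 split 2:2:1 (240, 240, 120), exact enumeration gives above 99.99% for 45% vs 10% and 98.9% for 30% vs 10%. The statement reproduces. It fixes the arm sizes but says nothing about DLQI.

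**Inputs from the documents**
- Range 0 to 30 and threshold 4 points (SAP 7.4.1.6).
- About 20% adolescents (SAP 3): 0.20 × 600 = 120. CDLQI is for ages 12 to under 16, so it covers at most about 120 people, or 48 per active arm and 24 on vehicle. DLQI covers at least about 480, or 192 per active arm and 96 on vehicle.

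**Assumptions, because the documents give no figure**
- Share f with baseline below 4: 5% to 30%, equal across arms in expectation through randomization.
- Response among those able to respond: 70% vs 50%, with two alternatives below.
- Nominal two-sided 0.05, every participant observed at Week 8.

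**Formulas.** Unrestricted: n participants with rates p(1 − f). Restricted: n(1 − f) participants with rates p. Power = Φ(d/SE − 1.96), where d is the difference in rates and SE = √[p₁(1 − p₁)/n₁ + p₂(1 − p₂)/n₂].

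**Why the larger set has less power.** In the unrestricted set, (d/SE)² = d²(1 − f) / Σ[p(1 − p(1 − f))/n], with d the undiluted difference. In the restricted set it is d²(1 − f) / Σ[p(1 − p)/n]. Since 1 − p(1− f) exceeds 1 − p, the unrestricted ratio is always the smaller one. The direction therefore does not depend on the assumed rates.

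**Worked case, DLQI, f = 20%**
- Unrestricted: rates 0.70 × 0.80 = 56% and 0.50 × 0.80 = 40%. SE = √(0.56 × 0.44/192 + 0.40 × 0.60/96) = 0.0615. 0.16/0.0615 = 2.60, and Φ(2.60 − 1.96) = 74%.
- Restricted: 153.6 vs 76.8 participants. SE = √(0.21/153.6 + 0.25/76.8) = 0.0680. 0.20/0.0680 = 2.94, and Φ(2.94 − 1.96) = 84%.

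**DLQI, 192 vs 96, 70% vs 50% among those able to respond (odds ratio 2.33)**

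| f | Unrestricted rates | Difference | Odds ratio | Power, unrestricted | Power, restricted |
|---|---|---|---|---|---|
| 5% | 66.5% vs 47.5% | 19 points | 2.19 | 87% | 89% |
| 10% | 63% vs 45% | 18 points | 2.08 | 83% | 88% |
| 20% | 56% vs 40% | 16 points | 1.91 | 74% | 84% |
| 30% | 49% vs 35% | 14 points | 1.78 | 64% | 79% |

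**Other rates at f = 20%, same arm sizes.** With 60% vs 40%, the odds ratio goes from 2.25 to 1.96, and power is 76% unrestricted against 83% restricted. With 45% vs 25%, the odds ratio goes from 2.45 to 2.25, and power is 85% against 88%.

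**CDLQI, at most 48 vs 24, 70% vs 50%, f = 20%.** Unrestricted: 0.16/0.123 = 1.30, power about 25%. Restricted: 0.20/0.136 = 1.47, power about 31%.

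**The case against.** The strongest reply is that the proportion of all randomized participants who improve by at least 4 points is a legitimate ITT quantity. It is not wrong, only a different estimand, and the dilution is conservative. That stands, and it is why the full-ITT proportion should stay as a supportive result.

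The endpoint is also modest. SAP Table 1 and Protocol Table 5 list only change from baseline in DLQI; the responder analysis enters in SAP 7.4.2.3. It is outside the testing procedure of SAP 3.2 and outside the sample size basis. The ANCOVA of mean change is unaffected. The companion ≥ 2- and ≥ 3-point itch responders in 7.4.2.3 have no stated floor either. All of this stands and limits the weight of the point.

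A reader might infer more than the documents support:
- **That the ITT label in Appendix A proves the omission.** It does not. Itch Table 2.3.3 is also labelled ITT with no floor in its title, although 7.3.1.1 restricts that endpoint. The evidence is the absence of any condition in 7.4.1.6 and 7.4.2.3, set against 7.3.1.1.
- **That the SAP restricts itch because low scorers cannot respond.** Section 7.3.1.1 gives no reason.
- **That the PROMIS endpoints are a precedent.** They carry a baseline condition of at least 6, but those totals start at 8, so it removes nobody.
- **That all four tables lose power.** The LTS tables are summaries, so only their rates are affected.
- **That 240 vs 120 is the right size.** The two instruments are tabulated separately, so each table has fewer. DLQI and CDLQI are also missing from the list of nonresponder-imputed outcomes in 7.4.2.3, so even these numbers are not assured.
- **That treatment arms are biased or Type I error inflated.** Baseline precedes treatment and f is balanced by randomization.

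**Conclusion.** The point holds as a minor one. As written, the Week 8 DLQI and CDLQI responder analyses include participants who cannot meet the definition, and nothing in either document removes them. The loss of precision is certain in direction whenever anyone starts below 4.

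Its size is not known, because it rests on an assumed f and assumed response rates. For DLQI at 70% vs 50%, the power cost runs from about 2 points at f = 5% to about 15 points at f = 30%. If most participants have moderate disease, as the cap on IGA 2 implies, the lower end may be nearer the truth; the documents cannot settle this. For CDLQI the test has little power with or without a floor.

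No primary or key secondary conclusion is touched.

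**What to change.** In SAP 7.4.1.6 or 7.4.2.3, and in Tables 2.10.4.1 and 2.10.4.2, restrict the ≥ 4-point responder analysis to participants with a Day 1 baseline of at least 4 on the instrument they completed. Report the number excluded per arm. Keep the full-ITT proportion as a supportive result and leave the mean-change analyses in full ITT.

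If the filter is extended to the LTS summary Tables 2.10.4.3 and 2.10.4.4, say which baseline it uses. SAP 4.1.3 resets baseline for participants who cross over from vehicle, so an unspecified filter would mix Day 1 and start-of-LTS values across the LTS groups.

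The cost is one sentence and a filter on data already collected before treatment, so the randomized comparison is preserved. The downside is a smaller denominator and a result that describes only participants able to respond.
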